6. STUDY TREATMENT

All subjects entering the screening phase will receive a unique subject number. This number will be used to identify the subject throughout the study. Subjects withdrawn from the study retain their subject number. New subjects will be assigned a new subject number.

6.1 Treatments to be Administered

Lenalidomide will be administered for a total of 42 days. The starting dose will be 2.5 mg given orally every other day on days 1-21 of a 28-day cycle for 2 cycles. Dose escalations and de-escalations will be made until the MTD is reached.

To ensure subject safety in the dose-escalation portion of the study, an early stopping rule will be implemented in the event that a DLT rate of greater than 34% is observed at a dose level of 2.5 mg, the lowest dose level to be evaluated in this study. In the event a DLT rate of greater than 34% observed at the starting dose of 2.5 mg orally every other day, the study will be terminated.

The dose levels of lenalidomide will be as follows:

- Dose Level 1: 2.5 mg PO QOD Day 1-21 for 28-day cycle X 2 cycles
- Dose Level 2: 2.5 mg PO QD Day 1-21 for 28-day cycle X 2 cycles

- Dose Level 3: 5 mg PO QD Day 1-21 for 28-day cycle X 2 cycles
- Dose Level 4: 7.5 mg PO QD Day 1-21 for 28-day cycle X 2 cycles

Doses should be taken at approximately the same time each day.

Subjects must be instructed to swallow lenalidomide capsules whole with water at the same time each day. Do not break, chew or open the capsules.

If a dose of lenalidomide is missed, it should be taken as soon as possible on the same day. If it is missed for the entire day, it should not be made up.

Subjects who take more than the prescribed dose of lenalidomide should be instructed to seek emergency medical care if needed and contact study staff immediately.

6.2 Instructions for initiation of lenalidomide

Lenalidomide may begin if each of the following criteria are met:

- The ANC is ≥ 1.0 thou/mm³;
- The platelet count is ≥ 50 thou/mm³;
- The CD34+ donor chimerism is $\leq 90\%$ at day +60 or +120 (± 7 days) post-transplant.

Lenalidomide dosing will continue as scheduled unless a DLT occurs.

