	
9. Subjects must have total bilirubin ≤ 2 mg/dL;
 
10. Subjects must have serum AST and ALT levels ≤ 2.5 times upper limit of normal;
 
11. Subjects must have serum creatinine < 2.5 times upper limit of normal and a calculated creatinine clearance ≥ 30 ml/min by Cockcroft-Gault formula (see Appendix I: Cockcroft-Gault Creatinine Clearance Calculation);
 
12. All study participants who will receive lenalidomide based on the CD34+ chimerism testing must be registered into the mandatory Revlimid REMS[®] program, and be willing and able to comply with the requirements of the REMS[®] program;
 
13. Females of child-bearing potential (i.e., women who are premenopausal or not surgically sterile) may participate, provided they meet the following conditions:
 
a) Females of reproductive potential must adhere to the scheduled pregnancy testing as required in the Revlimid REMS[®] program; and
 
14. Written, voluntary informed consent, willingness, and ability to comply with all study procedures.
 
Exclusion Criteria:
 
 1. CD34- AML or MDS; 2. Subjects with peripheral blasts or progressive cytopenias will be excluded unless a CR or CRi confirmed by a bone marrow biopsy within two weeks post of the allo-HCT; 3. Inability to give informed consent; 4. Uncontrolled active infection(s) requiring intravenous antibiotics; 5. Known or suspected hypersensitivity to lenalidomide; 6. Grade II-IV acute GVHD or extensive GVHD; 7. Not able to swallow the lenalidomide capsule as a whole; or 8. Female subjects who are pregnant or nursing;

Accrual:
	
The sample size for the study is based on incidence of DLT; however, it is not to exceed 24 subjects. The accrual period will be three years.

Study Duration and Dates:
	
The subject recruitment period is approximately 36 months, starting last quarter 2015. The study duration encompasses the following:
 
 • Screening period of up to 14 days (+/-7 days from Day +60); and • The CD34+ donor chimerism will be performed on days +60 and +90 (± 7 days) post-transplant until the CD34+ donor chimerism drops to $\leq 90\%$. If the CD34+ donor chimerism continues to be $> 90\%$ by day +90 (± 7 days) post-transplant the patient will be removed from the study; • Treatment with lenalidomide will start within 10 days after detection of the CD34+ donor chimerism $\leq 90\%$ and be continued

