	
for 21 days in a 28 day cycle X 2 cycles or until terminating event occurs;
 
 In subjects receiving lenalidomide, the CD34+ donor chimerism will be performed at Days +60 and +120 (± 7 days) of lenalidomide therapy.
Safety Assessments:	
Subjects will be examined weekly per institutional standard of care. Examinations will consist of vital sign measurements, physical examinations, laboratory assessments (hematology, serum chemistries) and assessment of acute GVHD. NCI Common Terminology Criteria for Adverse Events (CTCAE), Version 4.0 will be used to grade toxicity and adverse events.
 
GVHD assessment: Acute GVHD will be evaluated as per institutional practice guidelines using established staging criteria (see Appendix F). GVHD severity will be determined clinically; however, biopsies of affected organs are encouraged whenever possible. GVHD assessments will be performed at screening and Days +60 & +90. If lenalidomide is initiated, GVHD assessments will be performed weekly during scheduled visits and continuing until 30 days after the last dose of lenalidomide. GVHD assessments will also be documented at Days +60 and Day +120 after the initiation of lenalidomide.
 
Overall grading and response to GVHD therapy will be measured through the use of the consensus and IBMTR GVHD severity indices based on physical exam and laboratory serum values (see Appendix F). Individual organ stages will be scored by the attending physician or other trained provider.

Immunosuppression:	All patients should receive standard GVHD prophylaxis per institutional guidelines per the treating physician.
Efficacy Assessments:	The efficacy outcome of interest will be reversal of the decreased CD34+ specific donor chimerism by day 60 of lenalidomide administration.

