Statistical Procedures:	This study is descriptive in nature and not designed to provide analytical inferential results regarding primary or secondary endpoints. The sample size is based primarily on clinical considerations and not on statistical power calculations. Statistical characteristics of the “3 + 3” design are described in Appendix G. Descriptive statistics will be used to summarize baseline subject characteristics, treatment administration, and safety variables. All subjects who receive at least 5 doses of lenalidomide and have one post-dose safety assessment will comprise the safety population. The efficacy evaluable population will comprise all subjects who complete

	at least 15 days of lenalidomide and have at least one post-therapy CD34+ specific chimerism assessment.
--	--

Schedule of Events

Assessment	Screening (+/-7 days from Day +60)	Post- Transplant Monitoring Days +60 & 90 (\pm 7 days)	Revlimid C1D1, C2D1	End of Treatment 30 Days post- last Revlimid Dose (\pm 2 days)	Post- Revlimid Monitoring Days +60 & +120 (\pm 7 days)	Survival Every 3-months for 1 year
Signed Informed Consent	X					
Demographics, Medical /Treatment History	X					
MDS and AML WHO Classification	X					
Weight, Height	X					
Physical Examination	X	X	X	X	X	
GVHD Assessment ^A	X	X	X	X	X	
Vital Signs	X	X	X	X	X	
Karnofsky Performance Score	X	X	X	X	X	
CBC + Differential	X	X	X	X	X	
Serum Chemistry	X	X	X	X	X	
Serum Pregnancy Test (females) ^B	X		X			
Bone Marrow Aspiration and Biopsy ^C	X					
Peripheral Blood Chimerism		X				
Peripheral blood CD34+ donor chimerism ^D		X			X	
Dispense Revlimid (21-day supply)			X			
Concomitant Medications	X	X	X	X		
Adverse Events Assessments	X	X	X	X		
Concomitant Blood Products	X	X	X	X		
Disease Response Assessment ^C	X	X				X
Survival Assessment				X		X

- A. Overall grading and response to GVHD therapy will be measured through the use of the consensus and IBMTR GVHD severity indices. GVHD assessments will be performed at screening and Days +60 & +90. If lenalidomide is initiated, GVHD assessments will be performed weekly during scheduled visits and continuing until 30 days after the last dose of lenalidomide. GVHD assessments will also be documented at Days +60, and Day +120 after the initiation of lenalidomide.

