- B. Females of reproductive potential must have 2 negative pregnancy tests prior to initiating therapy. The first test should be performed within 10-14 days, and the second test within 24 hours prior to prescribing REVLIMID therapy and then weekly during the first month, then monthly thereafter in women with regular menstrual cycles or every 2 weeks in women with irregular menstrual cycles.
- C. All disease assessments which occur during routine care of the subject will be recorded in the CRF. Bone marrow procedures or other disease assessments will be performed according to institutional guidelines or physician discretion.
- D. The peripheral blood CD34+ donor chimerism will be performed on days +60 and +90 (\pm 7 days) post-transplant until the CD34+ donor chimerism drops to \leq 90%. In subjects receiving lenalidomide, the CD34+ donor chimerism will be performed at Days +60 and +120 (\pm 7 days) of lenalidomide therapy. Additional CD34+ donor chimerism testing will be performed at the discretion of the clinical investigator (e.g., when a subject develops peripheral blasts, worsening pancytopenia, or extramedullary relapse).

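### The first-dose rule in section 6.2 accepts chimerism results from days +60 and +120 post-transplant, but the protocol tests at days +60 and +90, so a subject who first converts at day +90 does not qualify

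*Combined protocol and SAP*

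**What the plan says.** Section 6.2 (Instructions for initiation of lenalidomide) sets three conditions for the first dose and requires every one: ANC at least 1.0 thou/mm³, platelets at least 50 thou/mm³, and CD34+ donor chimerism of 90% or less "at day +60 or +120" (±7 days), expressly counted from transplant.

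The rest of the protocol gives a different second time point for the pre-treatment test:

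- Synopsis (Study Duration and Dates) and section 4.4: "The CD34+ donor chimerism will be performed on days +60 and +90" (±7 days) post-transplant, until the value falls to 90% or below. A subject still above 90% by day +90 leaves the study: "post-transplant the patient will be removed from the study". For those who convert, "Treatment with lenalidomide will start within 10 days after detection of the CD34+ donor chimerism" of 90% or less.
- Schedule of Events: the pre-treatment column is headed "Transplant Monitoring Days +60 & 90", and footnote D repeats it: "The peripheral blood CD34+ donor chimerism will be performed on days +60 and +90".
- Section 9.1.2: days +60 and +90 post-HCT.

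For chimerism testing outside 6.2, day +120 belongs to follow-up counted from the start of lenalidomide. The Synopsis and section 4.4 say "In subjects receiving lenalidomide, the CD34+ donor chimerism will be performed at Days +60 and +120" of therapy, and the matching Schedule of Events column is "Revlimid Monitoring Days +60 & +120".

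**The concern.** Section 6.2 is the rule that staff apply when deciding whether to give the first dose. It is not a summary of other sections: it sets its own platelet threshold (50 thou/mm³, against 30 for eligibility in section 5.2), so it has to be checked separately. If it omits day +90, a subject whose residual disease is first detected at the second scheduled test fails a written dosing condition, although section 4.4 plans for that subject to start within 10 days.

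The site then has two choices. It can withhold the drug from a subject the study means to treat, or it can dose and record a protocol deviation. The first runs against the protocol's own rationale of acting while tumor burden is low.

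The slip also works in the other direction. Section 6.2 names a day +120 result as acceptable, although a subject still above 90% at day +90 should already have been removed.

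**Working it through.** The plan states no figure to reproduce here. The check compares visit windows, each being the nominal post-transplant day ±7.

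| Time point | Window (post-transplant days) | Scheduled pre-treatment test? (Synopsis, Schedule of Events, 4.4, 9.1.2) | Accepted by 6.2? |
|---|---|---|---|
| +60 | 60 ± 7 = 53–67 | Yes | Yes |
| +90 | 90 ± 7 = 83–97 | Yes | No |
| +120 | 120 ± 7 = 113–127 | No | Yes |

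1. **Overlap.** Of the 15 days in the day +90 window, none lies in 53–67 or 113–127. Between the end of the +90 window and the start of the +120 window lie 15 full days (98–112). The visit tolerance therefore cannot bring a day +90 result within 6.2.

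2. **Whether a day +120 test could rescue the subject.** None is scheduled before treatment. Scheduled testing stops once a value of 90% or less is found, and anyone still above 90% by day +90 is removed. Additional tests are allowed at the investigator's discretion (footnote D, section 9.1.2), but 6.2 would accept such a result only if it fell in one of its two windows.

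3. **Whether waiting for the +120 window fits the 10-day start.** If detection is dated to the blood draw, the latest start under 4.4 is 97 + 10 = day 107, before day 113. For the 10-day limit to reach day 113, detection would have to be dated 113 − 10 = day 103 or later. That is 103 − 97 = 6 days after the latest permitted draw, or 103 − 83 = 20 days after the earliest. The protocol does not state the assay turnaround. Even with a slow result, the day +90 value would still not qualify, and a repeat test would be needed.

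4. **Delay if a site did wait.** At least 113 − 97 = 16 days after the latest day +90 draw, and at least 113 − 83 = 30 days after the earliest.

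5. **After correction.** With 6.2 reading day +60 or +90, all 15 days of the day +90 window qualify, against 0 of 15 now.

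**The case against.** The best case against giving this weight is that it is a one-number slip whose intended meaning is easy to recover. The Synopsis, the Schedule of Events with its footnote D, section 4.4 and section 9.1.2 all say +90. The removal rule makes sense only if a day +90 result of 90% or less leads to treatment. An investigator who compares the sections would probably read +90.

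It is also fair to say that section 4.4 gives a start window and not an unconditional duty to dose: a day +90 converter must still meet the ANC and platelet limits in 6.2 and may properly go untreated on those grounds. Finally, no analysis population or primary or secondary analysis depends on which post-transplant test triggered treatment.

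All of this stands as a limit on the consequences, but it does not remove the contradiction. No section corrects 6.2, and the sentence is complete and labels its days as post-transplant. Treating its wording as merely permissive would make the ANC and platelet limits optional too. A first-dose criterion should not require staff to overrule its text.

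**Conclusion.** The concern holds. Section 6.2 contradicts the testing schedule and section 4.4: one of the two scheduled pre-treatment tests cannot lead to treatment under the rule as written, and the other time point that 6.2 accepts is never scheduled before treatment. That conclusion needs only the stated days and ±7-day windows. The day-107 limit additionally assumes that detection is dated to the draw, but the conclusion does not depend on it.

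That +120 was carried over from the on-treatment schedule is an inference, though a strong one. How many subjects would first convert at day +90 cannot be determined from the document. The consequence is confined to who may be dosed and to protocol deviations. It does not extend to the DLT rules, the MTD determination or the sample size.

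**What to change.** In section 6.2, replace day +120 with day +90, so that the chimerism criterion accepts a value of 90% or less at day +60 or +90 (±7 days) post-transplant. Leave the on-treatment assessments at days +60 and +120 of lenalidomide unchanged.

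The cost is a one-line protocol amendment, with no added tests or visits. The same amendment could usefully state whether a discretionary test outside both windows may trigger treatment. The number change does not settle that question, and the correction does not depend on it.

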6.3 Management of Toxicity

Lenalidomide at higher doses can cause hematopoietic toxicities. Management of neutropenia, neutropenic fever, thrombocytopenia, anemia, bleeding, infection, nausea, vomiting, mucositis, enteritis, and/or diarrhea will follow standard guidelines within the institution.

6.3.1 Hematopoietic Supportive Care

Platelet transfusions should be given to maintain counts $> 10,000/\mu\text{L}$. Platelets should not be transfused electively on study if the patient has a platelet count $\geq 20,000/\mu\text{L}$ and has no other medical indication for platelet transfusion (for example, bleeding, surgical procedure). For patients with platelet count of $< 20,000/\mu\text{L}$, elective platelet transfusions will be given as necessary according to institutional guidelines (depending on the threshold level for transfusion at the institutions and individualized based on concurrent medical problems).

All blood and platelet transfusions will be recorded on the CRF.

6.4 Method of Treatment Assignment

The dose of lenalidomide will be assigned according to the dose escalation schedule in [section 4.2](#) and the dose level description in [section 6.1](#).

6.5 Record of Administration

Each subject will keep an accurate record of lenalidomide dosing on the Subject Dosing Diary. This diary will be kept in the research record as source documentation of lenalidomide dosing. Study personnel will review the dosing instructions with each subject at each study visit. Subjects will be asked to bring any unused drug and empty drug containers to the study site at the next visit for reconciliation with the Subject Dosing Diary.

Any unused Revlimid[®] (lenalidomide) will be returned to the site for disposition in accordance with Celgene's Revlimid Risk Evaluation and Mitigation Strategy[™] (REMS) (formerly known as RevAssist[®] Program).

7. CONCOMITANT MEDICATIONS

7.1 Concomitant Medications and Therapy

Any therapy or medication (except study drug), administered from screening until 28 days after the last dose of study drug, is considered a concomitant therapy or medication. If the use of any concomitant treatments (medications or procedures) becomes necessary, the treatment must be recorded, including the name of the drug or treatment, dose, route, date, indication for use, and frequency of treatment.

No other investigational drugs may be administered.

Concomitant medications should be kept to a minimum during the study. However, if these are considered necessary for the study subject's welfare and are unlikely to interfere with the study drug, they may be given at the discretion of the treating physician. Subjects may receive blood transfusions and ongoing supportive and palliative care (*e.g.*, pain control) as clinically indicated throughout the study. Anti-emetics and other supportive medications such as antibiotics should be recorded on the CRF. The administration of prophylactic antimicrobials is left to the discretion of the treating physician.

7.2 Excluded Medications

The following drugs are excluded:

- azacitidine (Vidaza);
- decitabine (Dacogen);
- Other investigational drugs.

7.3 Immunosuppression

All patients should receive standard GVHD prophylaxis per institutional guidelines per the treating physician.

8. STUDY PROCEDURES

8.1 Protocol Procedures

All subjects will have study-related procedures as described in the Schedule of Events table.

9. DATA MEASUREMENTS AND METHODS OF COLLECTION

9.1 Data Measurements

9.1.1 Safety Data

Safety variable for this study include the following:

- DLTs;
- Physical examinations including assessment of skin GVHD;
- Vital signs;
- Clinical laboratory measurements, including hematology and serum chemistry; and
- Adverse events.

9.1.2 Correlative Studies

The CD34+ specific chimerism analysis from peripheral blood will be performed on days +60 and +90 (± 7 days) post-HCT until the CD34+ donor chimerism drops to $\leq 90\%$ and/or on days +60 and +120 (± 7 days) days after the initiation of lenalidomide. Additional CD34+ donor chimerism testing will be performed at the discretion of the clinical investigator (*e.g.*, when a subject develops peripheral blasts, worsening pancytopenia, or extramedullary relapse).

9.2 Methods of Collection

9.2.1 Sample Collection for Correlative Studies

9.2.1.1 Blood Samples

Peripheral blood samples will be obtained by venipuncture or from venous catheter (if in place) and will be collected at the same time as other laboratory assessments are drawn for necessary clinical care, if possible. The risks of drawing blood from a vein include discomfort at the site of injection, bruising and/or swelling around the injection site, infection, or syncope from the procedure.

Approximately 50 mL of blood will be collected at each time point for the CD34+ specific chimerism testing.

9.2.2 Safety Measurements

Safety measurements for this study include AEs, clinical laboratory measurements (hematology and blood chemistry), physical examination findings, GVHD assessments, and vital signs.

9.2.2.1 Adverse Events

Prior to initiation of lenalidomide therapy, only serious and non-serious adverse events deemed to be related or possibly related to study interventions will be recorded as adverse events for the study. Adverse events will be collected at each clinic visit based on observation and spontaneous reporting.

9.2.2.2 Clinical Laboratory Measurements

All clinical laboratory assessments are outlined in the Schedule of Events.

Hematology assessments will be performed at Screening and then weekly during lenalidomide administration and for 3 weeks after therapy is completed. The hematology assessments will include:

- Complete blood count including hemoglobin, hematocrit, WBC absolute differential and platelet count.

Blood chemistry assessments will be performed at screening and then weekly during lenalidomide administration. The chemistry assessments will include:

- Electrolytes: (sodium, potassium, calcium, magnesium, phosphorous, bicarbonate, and chloride);
- Renal function: (BUN, creatinine, and uric acid);
- Liver function: SGOT (also known as AST), SGPT (also known as ALT), total bilirubin; and
- Alkaline phosphatase.

Serum pregnancy test for females of childbearing potential will be performed at Screening and must follow the pregnancy testing requirements as outlined in the Revlimid REMS® program material.

Abnormal values and/or noteworthy changes will be graded according to the Common Terminology Criteria for Adverse Events v4.0 (CTCAE).

Abnormalities of laboratory values:

The Investigator shall classify laboratory values occurring outside of the normal range obtained for the safety assessment as:

- “Abnormal, but not clinically significant” or
- “Abnormal and clinically significant”

Laboratory abnormalities should be judged as “clinically significant” if they lead to treatment modifications, therapeutic actions, or if additional diagnostic measures are required for their resolution and in the Investigator’s opinion is relevant for the clinical study.

Each clinically relevant laboratory abnormality must be recorded as a separate AE if it fits within the AE criteria outlined in Section 10.1 of the protocol and is not already described by another documented AE.

Hematology and serum chemistry assessments will be performed according to the standard operating procedures by the validated local laboratory.

